The treatment groups for both participants with UC and healthy controls will be instructed to modify their current dietary intake by replacing a portion of their fat intake with extra virgin olive oil (EVOO) over a 4-weeks. We will aim to replace all free fats or fats added into meal preparation which includes but is not limited to cooking oil, fat spreads, butter, and oil based dips and sauces. For the purposes of this study, we will aim to ensure that energy intake between participant's usual diet and the intervention remains the same. As such, average energy contributions of free fats in the diet will be calculated, which will then be converted to the quantity of EVOO required to be consumed daily. Kitchen weight scales and marked bottles will be used to assist estimating the participant's daily requirement. The study dietitian will provide information on strategies to incorporate the oil into the participant's daily meals and a checklist for daily intake to assist with the behaviour change. If the participant is fasting for any reason during the study, the intervention will resume once the participant is able to consume meals again. No top ups from previous days will be required. For participants with shared meal preparation responsibilities in the household, additional bottles of EVOO will be provided. The EVOO used for this study will be Australian produced EVOO currently available for sale as a food item in accordance with Australian food regulations and will not be a special product or formulation. Upon completion of the 4 weeks of the intervention, all remaining EVOO bottles will be collected and participants will be requested to return to consuming their regular diet. During this 4-week washout period, participants will resume their usual intake of free fats to identify any sustained effects of the intervention.

Both during active intervention and the washout period, participants will be requested to maintain all their daily activities including physical activity, sleep and exercise. All of the documentation of changes in health care, habitual exercise or diet noted for the control group below will also be recorded in the intervention group.

Control Group: Usual Care

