6.5 STATISTICAL ANALYSIS

Intention-to-treat analysis regardless of dropout or study adherence is the primary analytic strategy. Primary and secondary continuous outcomes will be analyzed via linear repeated measures mixed models for testing of Group X Time interaction, with covariate adjustment over baseline and 4 weeks to characterize the intervention effects. In addition, outcomes at 5-8 weeks will identify and characterize any residual effects of the intervention during the washout phase and will be analyzed with respect to the intervention changes to determine the time course, if any, of residual effects. Covariates selected *a priori* based on the literature include age, sex, macronutrient intake, energy intake, and habitual physical activity level; other potential confounders identified at baseline may be added as required. A mediation analysis will be conducted via the PROCESS macro for SPSS version 2.13.2 to determine the indirect effect of dietary change on objective and subjective outcomes mediated by hypothesized beneficial alterations in the gut microbiota, while accounting for any potentially direct effects of EVOO.

[figure not shown]

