2 Weeks	Baseline Clinic Visit 2 (must be at least 8 days after Clinic 1)	
In person physical and health screen (duration ~5-6 hours)
 
 - Fasted assessments - Anthropometry - Collection and review of assessment 1 forms 
Location: The University of Sydney, Faculty of Health Sciences, Lidcombe

	
Randomisation into 1 of 4 Groups (UC Usual Care, UC Intervention, Control Usual Care, Control Intervention)
	
4 Weeks	Intervention (Week 1-4)	
Intervention: Replacement of usual free fats with the study fats
 
Usual Care: Maintain all usual daily activities
 
Weekly teleconference for all study groups (duration 15-20 minutes) Review new symptoms, changes to current therapy, lifestyle, visits to a healthcare professional

2 Weeks	Mid-Point Assessment (Week 5, over 2 days)	
Repeat a portion of assessments in Clinic Visit 1 and Clinic Visit 2
 
 - Fasted assessments - Nutrition assessment & food diaries - Stool collection - Questionnaires 
Location: The University of Sydney, Faculty of Health Sciences, Lidcombe

4 Weeks	Washout Period (Week 6-9)	
Intervention 1 and 2: Collection of all unused study fats, resume usual daily behaviour prior to study
 
Usual Care: Maintain all usual daily activities
 
Weekly teleconference for all study groups (duration 15-20 minutes) Review new symptoms, changes to current therapy, lifestyle, visits to a healthcare professional

2 Weeks	Final Assessment Clinic Visit 1	
In person physical and health screen (duration ~3-4 hours)
 
 - Physician review (as required) - Questionnaires (food intake, IBD symptoms, affect) - 3-day Weighted Food Diary Instruction - Stool Collection Instructions - 7-day Axivity Monitor Attachment 
Location: The University of Sydney, Faculty of Health Sciences, Lidcombe

	Final Assessment Clinic Visit 2 (must be at least 8 days after Clinic 1)	
In person physical and health screen (duration ~2-3 hours)
 
 - Fasted assessments - Anthropometry - Collection and review of assessment 1 forms 
Location: The University of Sydney, Faculty of Health Sciences, Lidcombe

End of Study Participation		

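### The protocol does not say whether participants are still on olive oil when the '4-week' samples are taken: EVOO stops after week 4, sampling is in week 5, and Figure 2 starts washout only in week 6

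*Protocol*

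**What the plan says.** - **Protocol, Section 6.2 (treatment group).** EVOO is taken for four weeks. Then: "Upon completion of the 4 weeks of the intervention, all remaining EVOO bottles will be collected and participants will be requested to return" to their regular diet. The next sentence reads: "During this 4-week washout period, participants will resume their usual intake of free fats to identify any sustained effects of the intervention".
- **Protocol, Section 6.5.** The mixed model is fitted "with covariate adjustment over baseline and 4 weeks to characterize the intervention effects", and "outcomes at 5-8 weeks will identify and characterize any residual effects of the intervention during the washout phase".
- **Protocol, Section 7.1, Figure 2.** The intervention row is weeks 1-4. The next row is "Mid-Point Assessment (Week 5, over 2 days", containing fasted assessments, nutrition assessment and food diaries, stool collection and questionnaires. It says nothing about diet. The row after that is "Washout Period (Week 6-9", and only there does the figure list "Collection of all unused study fats, resume usual daily behaviour prior to study". The final visits follow, with "Final Assessment Clinic Visit 2 (must be at least 8 days after Clinic 1".
- **Protocol, Section 9.1.** Outcomes are labelled baseline, 4 weeks and 8 weeks. The gut microbiome is a primary outcome alongside the Partial Mayo Score.
- **Protocol, Section 4.** Aim 4 asks about residual effects four weeks after the intervention.

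**The concern.** Week 5 is washout in Section 6.5 and precedes washout in Figure 2. The mid-point is the only clinic assessment between baseline and the final visits, so it alone can supply the 4-week stool, blood and diary data, and it falls in the week on which the two sections disagree.

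The measures at risk are those that a short return to usual fats could change: the stool microbiome, the blood and faecal markers (including plasma oleic acid and the olive phenols) and the 3-day food diary. If EVOO stops at the end of week 4, the sample meant to show the effect of EVOO is taken after it has ended, and the persistence question (Hypothesis 4) compares two time points that are both off EVOO. Only the EVOO arm can lose exposure, so any short-lived contrast would shrink. If staff follow different sections for different participants, on-EVOO and off-EVOO samples carry the same label. No later analysis can separate them unless stop dates are recorded.

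**Working it through.** Day 1 is the first EVOO day, weeks have 7 days, and days off EVOO = sample day − last EVOO day.

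**1. The plan's own washout window.** Four weeks of EVOO (Section 6.2) are days 1-28. A 4-week washout straight afterwards is days 29-56, which is weeks 5-8, as Section 6.5 says. A visit on day 56 would be 56 − 28 = 28 days off EVOO, which agrees with Aim 4 and the 8-week label. Sections 4, 6.2, 6.5 and 9.1 therefore fit together.

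**2. Figure 2's calendar.** By its week labels, the mid-point (week 5) is days 29-35, washout (weeks 6-9) is days 36-63, and the final visits start on day 64, in week 10. This does not reproduce weeks 5-8.

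**3. Mid-point samples under each reading.**

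| Reading | Last EVOO day | Mid-point samples, days 29-35 | Exposure |
|---|---|---|---|
| Section 6.2's stop with Figure 2's visit week | 28 | 29 − 28 = 1 to 35 − 28 = 7 days off EVOO | 28 days |
| Figure 2's order, EVOO until washout starts | 35 at the latest | on EVOO | up to 35 days; 35/28 − 1 = +25% |

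**4. Final visits on Figure 2's order.** The final row is marked as two weeks, so days 64-77. Visit 2 is at least 8 days after visit 1, so visit 1 is on days 64-69 and visit 2 on days 72-77. With EVOO ending on day 35, visit 1 is 64 − 35 = 29 to 69 − 35 = 34 days off, close to Aim 4. The fasted visit 2 is 72 − 35 = 37 to 77 − 35 = 42 days off. Stool instructions are given at final visit 1, and the baseline procedure lists stool under day 2, so the final stool comes after visit 1 and possibly on the day of visit 2.

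**5. Visit spacing and the fix.** Section 9.1 requires 7-day accelerometry at 4 weeks, so the mid-point probably needs two visits about a week apart. No gap is stated for it. Figure 2 gives at least 8 days for baseline and final visits; the text of Section 7.1 gives at least 7 for baseline. Applying either to the mid-point is an assumption.
- First visit on day 29, 8-day gap: sampling on day 29 + 8 = 37 at the earliest. Keeping EVOO until then gives 37/28 − 1 = +32%.
- First visit on day 22 (start of week 4): sampling from day 22 + 7 = 29 or 22 + 8 = 30, that is 29/28 − 1 = +4% or 30/28 − 1 = +7%.
- Sampling on day 28 or 29 with an 8-day gap: first visit on day 28 − 8 = 20 or 29 − 8 = 21, the end of week 3.

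**The case against.** The strongest defence is that the documents allow one workable sequence. Section 6.2 and Figure 2 agree on four weeks of EVOO, then bottle collection, then a four-week washout. The mid-point is the only clinic attendance between intervention and washout, so it is the natural place to return the bottles. On that view, 4 weeks, 8 weeks and weeks 5-8 are nominal labels that ignore the visit window. In addition, both arms share the visit schedule, and the sample size rests only on the Partial Mayo Score, which is also collected weekly.

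Much of this stands. The off-EVOO result arises only if Section 6.2's stop is paired with Figure 2's visit week. Visit timing does not differ by arm, and the disease-activity outcome is largely protected. But no section says that the bottles come back at the mid-point visit or that EVOO continues until then, and weeks 5-8 and weeks 6-9 cannot both be right. This is an instruction to staff and participants; an analysis plan cannot change when a sample was taken.

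Three stronger readings are tempting, and the documents do not support them:
- **That the 4-week samples are certainly off EVOO.** The protocol leaves this open.
- **That the mid-point lasts two weeks, giving up to 14 days off EVOO or 42 days of exposure.** This relies on a duration cell reading 2 weeks. Figure 2's own labels contradict it: a two-week mid-point would put washout in weeks 7-10, not 6-9. The cell may be a scheduling allowance.
- **That the final samples come six or seven weeks after EVOO stops.** This pairs Section 6.2's stop with Figure 2's later calendar. Section 6.2's own washout ends on day 56, 28 days after the stop.

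**Conclusion.** The point holds as a contradiction in the schedule that should be fixed. As written, the 4-week microbiome, blood and diary measures may be taken 1-7 days off EVOO, or on EVOO after up to 35 days rather than 28. On Figure 2's order, the final fasted visit is about 37-42 days after EVOO ends rather than four weeks.

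The figures assume 7-day weeks counted from the first EVOO day and Figure 2's week labels; the 42 also assumes that the final row lasts two weeks. How far a few days off EVOO would dilute the effect cannot be derived from the documents. The point does not show that the trial is invalid or biased between arms by visit timing, and it changes no sample-size figure.

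**What to change.** State one rule in Sections 6.2, 6.5 and 9.1 and in Figure 2:

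1. EVOO continues until the last mid-point stool, blood and diary collection is complete. Bottles are collected at that visit.
2. Washout is the 28 days after the last EVOO day, replacing both weeks 5-8 and weeks 6-9.
3. The final stool and fasted blood are taken about 28 days after the last EVOO day.
4. Usual care follows the same timing, counted from the mid-point sampling visit.

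To keep exposure close to 28 days, hold the first mid-point visit (diary and stool instructions, monitor fitting) at the start of week 4, or a day or two before if the 8-day gap applies. Fasted sampling then falls at about day 28-30. Leaving the first visit in week 5 with that gap would mean at least 37 days of EVOO.

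**Cost.** Wording in four places, with no added visits, samples or participants. Booking becomes tighter and exposure may run slightly over 28 days. With an 8-day gap, final visit 1 moves to about day 28 − 8 = 20 of the washout or earlier, so it falls inside the washout, along with its as-required physician review. Moving the recall questionnaires and the clinic Partial Mayo to the sampling visit is optional and not needed to resolve the contradiction.

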7.1.1 Eligibility Criteria

We will recruit men and women aged ≥ 18 years with Ulcerative Colitis who are able to provide written informed consent will be recruited from gastroenterologists as well as via community/social media advertising in the greater Sydney area.

Participants with UC Inclusion Criteria:

1. Aged ≥ 18 in 2018
2. Ulcerative colitis (UC) >3 months duration of any extent.
3. Stable medication. No planned changes to current medication and therapies during the study period, and no changes to medication in the preceding 4 weeks.

Participants with UC Exclusion Criteria:

1. Prior or concomitant fecal microbiota transplantation or any rectal preparations currently.
2. Antibiotic/anti-tuberculosis treatment for any reason during the study period or in the preceding 4 weeks.
3. Probiotic supplements or biological/monoclonal antibody agents during the study period or in the preceding 12 weeks. Food based probiotics such as yoghurt and kefir will be allowed.
4. Significant prior gastrointestinal surgery (e.g., colon resection, colectomy, appendectomy) or clinical evidence of any comorbid chronic disease that may interfere with the patient's ability to enter the trial and undertake the intervention planned.
5. Coexistent serious autoimmune disease such as rheumatoid arthritis or systemic sclerosis.
6. Planned major surgery within the first 3 months after randomization.
7. Pregnancy or female planning pregnancy within the first 3 months after randomization.
8. Participation in another clinical trial for with concurrent participation is deemed inappropriate.
9. Daily consumption of olive based product(s) in any form (including oil, pickles, tapenade, spreads, and supplements) as determined by the diet history and medication list
10. Currently on a special diet in which participation is deemed inappropriate (e.g. low residue diet, liquid diet, low fat diet)

We will also recruit men and women aged ≥ 18 years with no significant chronic or acute disease who are able to provide written informed consent to participate in the study as the healthy control group. Recruitment will be achieved through community/social media

advertising in the greater Sydney area alongside the recruitment strategy for participants with UC.

Healthy Control Inclusion Criteria:

4. Aged ≥ 18 years in 2018
5. Willing to be randomized into one of the two study arms and participate in the intervention prescribed
6. Stable medication. All drugs to be held at constant dose during the study and no changes to medication in the preceding 4 weeks.

Healthy Control Exclusion Criteria:

1. Those in remission from UC as defined by an assessment by a gastroenterologist.
2. History of fecal microbiota transplantation or any rectal preparations including enemas.
3. Antibiotic/anti-tuberculosis treatment for any reason during the study period or in the preceding 4 weeks.
4. Probiotic supplements or biological/monoclonal antibody agents during the study period or in the preceding 12 weeks. Food based probiotics such as yoghurt and kefir will be allowed.
5. Chronic or acute disease requiring medical or therapeutic intervention including but not limited to diabetes, IBD, chronic kidney disease, cancer, IBS.
6. Coexistent serious autoimmune disease such as rheumatoid arthritis or systemic sclerosis.
7. Significant prior gastrointestinal surgery (e.g., colon resection, colectomy, appendectomy) or clinical evidence of any comorbid chronic disease that may interfere with the patient's ability to enter the trial and undertake the intervention planned.
8. Planned major surgery within the first 3 months after randomization.
9. Pregnancy or female planning pregnancy within the first 3 months after randomization.
10. Participation in another clinical trial for with concurrent participation is deemed inappropriate.
11. Daily consumption of olive based product(s) in any form (including oil, pickles, tapenade, spreads, and supplements) as determined by the diet history and medication list
12. Currently on a special diet in which participation is deemed inappropriate (e.g. low residue diet, liquid diet, low fat diet) or under the supervision of an Accredited Practising Dietitian or other relevant healthcare professional

7.2 INFORMED CONSENT

During the telephone and in-person screening process, participants will be informed of the purpose of the screening, and what will happen to their data. Oral consent will be sought only to the answering of questions on our telephone screen. If participants respond that they are willing to answer the questions, this will constitute their verbal consent for those specific

questions only. If they refuse to answer the questions in its entirety, they are thus considered to have refused to give consent for the study, and the telephone screen will end. The telephone screen answers will be recorded directly in REDCAP by the research staff conducting the screen. These data will be exported to EXCEL/SPSS for tracking of study recruitment procedures and reporting of CONSORT flow of participants.

Post telephone screen, participants will be provided with a form outlining their intent on participating in the COLONIC Study which will need to be sent to their nominated healthcare provider(s). This step is critical to ensure that their participation in this study is not contra-indicated to the current care or therapy received, in addition to clarifying any ongoing therapies or treatment. If a participant is on hold prior to the in-person assessment, additional information from the participant's nominated healthcare provider(s) may be requested. Participants will be consulted and briefed prior to any communication being established, and all relevant health information will be kept confidential. Those deemed to be eligible and are still interested in participating will then be requested to attend an in person physical and health assessment at the University of Sydney Cumberland Campus C Block Clinic at a nominated date.

Prior to any assessments at the clinic, participants will be provided a copy of the Participant Information Statement (PIS) and an overview of the study schedule, assessments, and commitments will be provided including information on data confidentiality and withdrawals. This will be followed by a written, witnessed, and informed consent on participating in the COLONIC study by signing the Participant Consent Form (PCF).

7.3 CONFIDENTIALITY AND PRIVACY

Data will be collected over the phone (telephone screening) and in person (assessments), using researcher-administered questionnaires, and physical testing. Data gathered from the screening process, assessment, and training sessions will be entered by the research staff into a database created in REDCap. Data will be entered in a re-identifiable form using unique identity numbers. This code will be used on all electronic data forms, electronic databases and hard copy data forms. No forms will contain the names of participants, or other identifying information.

All participant information will remain re-identifiable, so that information that is relevant to their medical care can be communicated to appropriate medical professionals. Participants will only remain re-identifiable to persons directly involved with the study, namely the Primary and Associate Investigators or HDR students who are conducting the intervention/ assessments. All data will be de-identified prior to depositing in a repository at the end of the study, as required by the National Health and Medical Research Council.

During screening, participants will be assigned a Screening ID. Participants who are found eligible for the study and consent to participate will be randomised by an investigator who is otherwise not involved in the study. Participants will then be issued with a Study ID Code. The Screening ID Code and Study ID code will be recorded in the randomisation database.

The investigator performing the randomisation will only be provided with Screening ID, age, and gender of the participant to perform the randomisation procedure. Once randomised, participant ID codes will not be removed, even if they choose to withdraw from the study.

7.4 DATA STORAGE AND RETENTION

Electronic copies of information will be stored in two places:

1. CIA [name] [name]'s Research server maintained by the University of Sydney. This carrier will be used to store contact information, progress databases, digital copies of consent forms, medical letters, audio and video recordings, and correspondence and manuals of procedures. This is a password protected server only accessible to researchers involved in the project. Server back-up is performed by the university central server. All documentation will be password protected. REDCAP Digital is a secure web application hosted by The University of Sydney for building and managing databases. All data entered into the database will be stored on a secure server of the University of Sydney. As such, no project data is ever transmitted at any time by REDCap to another institution or third party.

Access to the database will be provided only to research staff working on the study. User privileges will be used to limit the viewing and/or editing access that research members have within the database. All access rights will be managed by the study coordinator at the University of Sydney. Furthermore, all data entry forms will use participant codes rather than names or other potentially identifying information.

Hard copies of the following information will be stored in the locations below:

1. Original copies of participant consent forms will be stored in a locked filing cabinet in secure lockable K block office K221 at the Cumberland Campus of the University of Sydney.
2. A back up hardcopy of assessment data (analogous to REDCAP digital data) will be stored in a locked filing cabinet in secure, lockable K block office K221 at the Cumberland Campus of the University of Sydney.

A complete dataset of REDCAP data will be downloaded, copied and stored securely on [name] [name]'s server at the University of Sydney. Hardcopy data will continue to be stored in a secure, lockable office in K block, K221.

Data collected in this study will be retained indefinitely in de-identified form with consideration of the novel nature of the study and potentially significant clinical importance of our findings. Additional projects involving long-term follow up study participants to investigate factors related to progression of inflammatory bowel disease, which may take an unknown number of years, may be considered. In the event that such a study is considered, the appropriate ethics amendment and consent forms will be required in consultation with HREC as has been done with previous longitudinal studies. There is also the potential for outcomes from this study to be pooled with other concurrent studies or future studies on other chronic gastrointestinal conditions which will also require the relevant ethics application or amendment.

